2.2.4.1 Nonclinical Studies

2.2.4.1.1 *In Vitro* Pharmacology

The comparison of *in vitro* functional activities of DRL_RI, Rituxan[®] and MabThera[®] was performed using multiple cell-based and binding assays. Batches of DRL_RI, Rituxan[®] and MabThera[®] were compared using Two One-Sided t-Test analyses. A difference of 20% in the mean relative binding or potency was deemed acceptable. The CDC and the ADCC activities and the binding of DRL_RI, Rituxan[®] and MabThera[®] to CD20, C1q, FcγRI, FcγRIIa, FcγRIIb, FcγRIII, and FcRn were found to be similar. Therefore, DRL_RI, Rituxan[®] and MabThera[®] are considered similar in terms of their *in vitro* functional characteristics.¹¹

2.2.4.2 Clinical Studies

The PK characteristics of DRL RI, MabThera[®], and Rituxan[®] were compared in a double -blind, randomised, 3 arm study CCI conducted in subjects with moderate to severe RA. The results of the study showed that the 91% CI for the test to- reference ratios of all pre-specified primary and secondary PK endpoints were within the pre-specified window of 80.00% to 125.00% for the comparisons of DRL RI to -MabThera® and Rituxan®, and for the comparison of MabThera[®] to Rituxan[®], demonstrating the PK similarity of the 3 products. The primary PK endpoints were area under the concentration-time curve (AUC) from time zero extrapolated to infinity for both study drug infusions, AUC from start to first infusion to the second infusion on Day 14 after the first infusion and AUC from time zero to the last quantifiable time point (AUC_{0-t}) after the second infusion of study drug. The secondary PK endpoints were AUC_{0-t} over the entire treatment course, and maximum plasma concentration (C_{max}) after the first and after the second infusion. The results also showed that the safety and immunogenicity profiles and CD20positive -Bcell- depletions as well as the proportion of subjects meeting the American College of Rheumatology (ACR)20, ACR50, and ACR70 improvement criteria from Baseline to Week 24 and the mean change from Baseline to Week 24 in Disease Activity Score 28-C-Reactive Protein (DAS28-CRP) were comparable across DRL RI, MabThera[®], and Rituxan[®].¹²

2.3 Benefit/Risk Assessment

There is a substantial body of data related to the safety and efficacy of Rituxan[®]/MabThera[®] in subjects with B-cell NHL (Food and Drug Administration [FDA] Rituxan[®] prescribing information/European Medicines Agency [EMA] MabThera[®] SmPC).^{1,2} A comprehensive head-to-head comparison of [name] rituximab antibody, DRL_RI, to the US-approved Rituxan[®], and the European RMP (MabThera[®]) has demonstrated that DRL_RI is similar to Rituxan[®] and the RMP (Section 2.2.4.2). Thus, the risk/benefit of DRL_RI is expected to be comparable to that of Rituxan[®]/MabThera[®].

More detailed information about the known and expected benefits and risks and reasonably expected adverse events (AEs) of DRL_RI may be found in the IB for DRL_RI.¹¹

3 Objectives and Endpoints

Objective	Endpoint			
Primary				
To demonstrate the equivalent efficacy of DRL_RI and MabThera [®] in subjects with B-lymphocyte antigen CD20-positive, LTB-FL, as measured by ORR up to Week 28, evaluated in accordance with published response criteria for malignant lymphoma.	The primary endpoint is BORR, defined as the proportion of subjects in each treatment group that achieve a best overall response of either CR, CRu or PR up to Month 7 (Week 28) based on central radiology review in accordance with the response criteria for malignant lymphoma. ¹³			
Secondary				
• To compare the ORR at Week 12 and Week 28, CR at Week 28, CR as a best response up to week 28, duration of response (DOR), PFS and OS of DRL_RI with MabThera [®] in subjects with CD20-positive, LTB-FL.	 Overall response rate at Week 12 and Week 28 based on central radiology review in accordance with published response criteria for malignant lymphoma¹³. Complete Response (CR) rate at Month 7 (Week 28). CR rate as a best response up to Month 7 (Week 28). Duration of response defined as the time from date of the first documentation of tumour response (CR, CRu or PR) to the date of first documentation of PD or to death due to any cause up to 52 weeks/EOS. Progression-free survival defined as the time from date of randomisation to the date of documented progressive disease (PD) or death due to any cause. Overall survival defined as the time from date of randomisation to the date of Study (EOS). 			
• To compare the safety, tolerability, and immunogenicity of DRL_RI with MabThera [®] in subjects with CD20-positive, LTB-FL.	 Adverse events, clinical laboratory values, vital signs, and electrocardiogram (ECG) Anti-rituximab antibodies and their relationship with other outcome measures. 			

	Objective		Endpoint
Exploratory			
•	To compare ORR evaluated in accordance with the Lugano criteria ¹⁴ in subjects with CD20-positive, LTB-FL treated with either DRL_RI or MabThera [®] .	•	Overall response rate based on the Lugano criteria ¹⁴ for those subjects with available positron emission tomography (PET) data.
•	To explore the PK parameters of DRL_RI and MabThera [®] , using a population-PK modelling approach.	•	Pharmacokinetic parameters (e.g., clearance and volume of distribution) for DRL_RI and MabThera [®] will be derived using a population-PK modelling approach.
•	To explore the pharmacodynamic parameters of DRL_RI and MabThera [®] .	•	Potential differences in pharmacodynamic parameters (e.g., area under the effect curve [AUEC] of circulating B-cells depletion) for DRL_RI and MabThera [®] will be investigated.

4 Study Design

4.1 Overall Design

4.1.1 Description

This is a Phase III, randomised, multicentre, double-blind, parallel-group study in subjects with previously untreated, Stage II-IV, CD20-positive, LTB-FL.

It is planned to randomise approximately 312 subjects (Please refer Section 9.2) at approximately \geq 130 study sites worldwide.

The study will enrol subjects with CD20-positive, LTB-FL who are asymptomatic for lymphoma specific B-symptoms. LTB-FL will be assessed according to the GELF based criteria.^{3,9}

Subjects will receive induction treatment consisting of a weekly i.v infusion for 4 weeks (375 mg/m² of BSA) followed by maintenance treatment consisting of an i.v infusion (375 mg/m² of BSA) every 8 weeks from Week 12 up to Week 36.¹⁵

Randomisation will be stratified by low-, medium-, and high-risk subjects using the CCI CCI CCI CCI CCI CCI CCI (1-2 Vs. 3a) and geographical area (USA, Europe and Asia-Pacific region).

Subjects will attend study visits every week (± 2 days) during the Induction Treatment Period (Weeks 1 to 4), at Week 8 (± 7 days), at Week 12 (± 7 days), thereafter every 8 weeks (± 7 days) up to Week 52 (EOS/Early Termination [ET] Visit). Study procedures include physical examination, vital signs, Eastern Cooperative Oncology Group (ECOG) performance status, tumour assessments, clinical laboratory tests, serum LDH and β-2 microglobulin, coronavirus disease 2019 (COVID-19) testing at screening and as deemed appropriate by the Investigator at any time during the study, AEs, concomitant medication, immunogenicity, and PK and pharmacodynamic samplings for the subjects in the corresponding subset.

All subjects completing the study (Week 52) will attend an EOS Visit. Subjects discontinuing the study before Week 52 for any reason will also attend an ET Visit. Subjects positive for hepatitis B at screening will be followed up to 24 months post last dose of rituximab in the study as outlined in Section 6.10.

Subjects with a prior history of hepatitis B infection or serological tests suggestive of previous hepatitis B infection will continue to receive hepatitis B virus (HBV) antiviral prophylaxis therapy for at least 12 months post last dose of rituximab in the study and will be monitored and reported

for reactivation for up to 24 months following completion of rituximab therapy as outlined in Section 6.10.

Subjects prematurely discontinued from treatment, but wishing to continue in the study, will return for an ET Visit 8 weeks after the last dose of study drug. The post-treatment discontinuation follow-up for subjects wishing to continue in the study is detailed below:

- If the reason for study discontinuation is disease progression, the subjects will be contacted by telephone for information on survival, AEs, and concomitant medications every 8 weeks, for a total observation period of 52 weeks.
- If the reason for study discontinuation is different from disease progression, subjects will continue to attend scheduled tumour assessments (at which AE and concomitant medication information will also be collected) up to disease progression or Week 52, whichever occurs first. If these subjects subsequently experience disease progression then they will continue to be followed up by telephone every 8 weeks from that point of identification and for a total observation period of 52 weeks, as described for subjects discontinued from study drug due to disease progression.

Clinical assessments will be performed before the start of each treatment cycle by the Investigator. Tumour assessments for the purpose of assessing subject eligibility and medical care will be performed by the investigational site at Screening and Weeks 12, 28, and 52 (EOS/ET Visit).

The primary endpoint is BORR, defined as the proportion of subjects in each treatment group that achieve a best overall response of either CR, CRu or PR up to Month 7 (Week 28, i.e., 6 months after completion of rituximab induction) based on central radiology review in accordance with the response criteria for malignant lymphoma.¹³ An exploratory analysis using the Lugano criteria¹⁴ will also be performed as described in Section 3 and Section 9.4.1.3.

Sparse PK sampling will be performed in a subset of approximately 90 subjects (approximately 45 subjects per treatment group) (PK and pharmacodynamic subset) on Days 1, 8, 15, 22, and at Week 12 (approximately 45 subjects per treatment group, these subjects will be included after they provide written consent for these evaluations) to facilitate a population-based PK approach using nonlinear mixed-effects modelling. At each of these visits, one sample will be taken prior to initiation of infusion (pre-dose or trough plasma concentration [C_{trough}]) and a second sample will be taken immediately prior to the end of the infusion. Indicatively, C_{trough} should be obtained within one hour prior to the start of infusion (but not after it has been started) and the sample prior to the end of infusion. In all cases the sampling time should be accurately recorded (date and time with hour and minutes). Should it not be possible to collect

the sample in the specified time frame, the sample should be anyway collected and the sampling date and time accurately (to hour and minutes) recorded.

The sampling date and time also needs to be accurately recorded for the samples obtained within the window period.

Separate samples for the pharmacodynamic marker, peripheral blood B-cell count, will be obtained in the same subset of subjects sampled for PK. These will be collected on the same days as the PK samples, as well as at Week 20, 28, 36, 44, and 52 visits, to facilitate a descriptive pharmacodynamic evaluation using the AUEC of B-cell depletion, B-cell counts at selected time-points, and optional population PK / pharmacodynamic modelling.

Samples for the evaluation of anti-rituximab antibodies (anti-drug antibodies [ADA]), including binding antibodies (BAb) and neutralising antibodies (NAb) will be obtained before the administration of study drug on Days 1 and 22. Additional samples for detection of BAb and NAb will be collected prior to study drug infusion at Weeks 8 and 28, as well as at the visits of Week 44 and Week 52 (EOS/ET Visit). Analysis of BAb samples will follow a tiered approach of screening and confirmation. Samples that are confirmed positive for BAb will be further tested for titre and NAb determination using validated assays.

Safety endpoints are the incidence of reported AEs and changes in vital signs, clinical laboratory parameters and electrocardiogram (ECG) parameters.

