4.11.2 Analysis of Adverse Events

All reported terms for AEs will be coded using the latest version of MedDRA version 21.1 or the latest. Before database lock the latest version of MedDRA will be used to code the AE terms for all study subjects. The US National Cancer Institute (NCI) Common Terminology Criteria for Adverse Events (CTCAE), version 5.0 (NCI-CTCAE version 5.0) will be used by investigator to assess the severity grade of all AEs.

For all AE tables, subjects will be counted once for each MedDRA PT and each SOC. Unless specified otherwise, AEs will be summarized in the alphabetical order of SOC and then decreasing frequency of PT within the SOC for the treatment group. If the frequency of PT within the SOC is tied, PT will be sorted alphabetically. Summaries by PT will be sorted by decreasing frequency according to the "DRL_RI" subject incidence.

TEAEs are defined as any AE occurring or worsening on or after the first dose of study treatment. AEs which are already present before the first study treatment and increase in severity after the first study treatment will be considered as TEAEs. Pre-existing AEs before the first study treatment with no increase in severity after the first study treatment will not be considered as TEAEs.

All treatment-emergent adverse events (TEAEs) will be summarized by SOC, PT and CTCAE grade, including the number and percentage of subjects experiencing events.

An overview of AEs by treatment group will be provided, including number of subjects experiencing TEAEs, drug related TEAEs, serious TEAEs, drug related serious TEAEs, TEAEs leading to discontinuation of study medication, drug related TEAE leading to discontinuation of study medication, TEAEs leading to death,. The summary will also be provided for subgroups age group (< $60, \ge 60$ years), gender and race.

Imputation of partial dates of AE record is described in Appendix 2 Partial Date Conventions.

[name] S.A	
Protocol RI-01-006	Statistical Analysis Plan

A by-subject listing of all AEs will be provided by treatment group and will include AE term (SOC, PT, and Verbatim term), start date/time and corresponding study day, end date/time and corresponding study day, severity, infusion related reaction (yes/no), relationship, action taken, outcome, seriousness including criteria of serious adverse event (SAE).

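### After the ET Visit, subjects who stop study drug for a reason other than progression are asked about AEs only at the remaining scans, up to 24 weeks apart, against every 8 weeks on the other routes

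*Protocol*

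**What the plan says.** Protocol 4.1.1 sets three schedules of AE contact. The Synopsis, Table 1-1 footnote 1 and Section 4.5 repeat the two routes after stopping, and Section 7.2 gives them in shorter form.

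- **On schedule.** Visits are weekly in induction, then at Weeks 8 and 12, and "thereafter every 8 weeks" to Week 52. AEs are assessed at each.
- **Stopped for progression.** After an ET Visit, subjects are "contacted by telephone for information on survival, AEs, and concomitant medications every 8 weeks, for a total observation period of 52 weeks". Section 4.5.1 lists the content of the call.
- **Stopped for another reason, staying in the study.** The subject "will return for an ET Visit 8 weeks after the last dose of study drug", and AE assessment is one of the EOS/ET procedures in Section 4.5. After that, "subjects will continue to attend scheduled tumour assessments (at which AE and concomitant medication information will also be collected", up to progression or Week 52. Tumour assessments are "performed by the investigational site at Screening and Weeks 12, 28, and 52".

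Protocol 8.4.2 requires all AEs to be recorded to the EOS Visit or, after early termination, to the later of the ET Visit and Week 52.

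On the analysis side, SAP 4.11.2 states that "TEAEs are defined as any AE occurring or worsening on or after the first dose of study treatment". It sets no end date relative to the last dose. Subjects count once per preferred term and once per system organ class. The AE sections describe no rate adjusted for follow-up time and no summary by discontinuation status.

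**The concern.** How often a subject is asked about AEs after stopping depends on why the subject stopped. The group asked least often includes those who stopped because of toxicity. The duty to record AEs to Week 52 is the same for everyone, but between scans no contact is scheduled for this group.

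Two things are at stake. The first is safety follow-up: a new event may be reported late or, if minor, forgotten. Protocol 8.4.11 asks for an SAE report of a death within 16 weeks after the last dose. For a last dose at Week 20 that window closes at Week 36, inside the Week 28 to 52 gap. For a last dose at Week 28 it closes at Week 44, inside the Week 36 to 52 gap. The second is the comparison of safety between the products, a secondary objective. The TEAE tables combine time that was ascertained at different frequencies, and nothing in them shows this.

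**Working it through.** The plan states no gap length, so there is no figure of its own to reproduce. The inputs are the nominal weeks in Protocol 4.1.1 and Table 1-1: scans at 12, 28 and 52; visits from Week 12 at 12, 20, 28, 36, 44 and 52; ET Visit at last dose + 8.

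**Scan-to-scan gaps:** 28 − 12 = 16 weeks; 52 − 28 = 24 weeks.

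**Calendar by last dose, with the ET Visit included:**

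| Last dose | ET Visit | AE contacts after last dose | Gaps (weeks) | Planned contacts, Weeks 12–52 (6 on schedule) | Contacts from ET to Week 52: now → with 8-weekly calls |
|---|---|---|---|---|---|
| Week 4 | Week 12 | 12, 28, 52 | 8, 16, 24 | 3 (12, 28, 52) | 3 → 6 |
| Week 12 | Week 20 | 20, 28, 52 | 8, 8, 24 | 4 (12, 20, 28, 52) | 3 → 5 |
| Week 20 | Week 28 | 28, 52 | 8, 24 | 4 (12, 20, 28, 52) | 2 → 4 |
| Week 28 | Week 36 | 36, 52 | 8, 16 | 5 (12, 20, 28, 36, 52) | 2 → 3 |

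A last dose at Week 1, 2 or 3 puts the ET Visit at Week 9, 10 or 11, followed by 12, 28 and 52. The long gaps are the same as for Week 4. The last column gives 3, 2, 2 and 1 extra calls, after which the longest gap is 8 weeks.

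**Which report is affected.** SAP Section 1 limits the first report to data up to Week 28. Within it, a subject whose last dose is at Week 12 is seen at 12, 20 and 28, as on schedule. Only induction stoppers have a longer gap (16 weeks, from 12 to 28). The 24-week gap lies wholly after Week 28 and affects only the Week 52 report.

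**Size, by assumption only.** Let s be the share of an arm that stops for non-progression reasons and stays in the study, q the share of these with a new event of a given type in the long gap, and m the share of such events missed. The loss in one table row is s × q × m. None of the three is in the documents. I take s = 5–20%, q = 10–30% and m = 10–50%, with 156 subjects per arm (Protocol 9.2).

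- Low end: 0.05 × 0.10 × 0.10 = 0.0005, or 0.05 percentage points; 156 × 0.0005 = 0.08 subjects.
- High end: 0.20 × 0.30 × 0.50 = 0.03, or 3.0 points; 156 × 0.03 = 4.7 subjects.
- Between arms, if s differs by 5 points, at the highest q and m: 0.05 × 0.30 × 0.50 = 0.0075, or 0.75 points.

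**The case against.** The strongest reply is that scheduled contact is not the only route by which an AE is captured. Protocol 8.4.2 has all AEs recorded to Week 52 with start and stop dates, and drug-related AEs followed past the ET Visit until stabilised, resolved or judged unlikely to resolve. Section 8.4.8 has SAEs followed to resolution, stabilisation or another explanation unless the subject is lost. Section 8.4.9 has SAEs reported within 24 hours of awareness. Section 4.1.2 allows unscheduled visits, and Section 8.5.1 encourages telephone inquiry. The SAP also does more than one pooled table: 4.11.2.2 splits TEAEs by onset in induction and maintenance, and 4.11.2.6 tabulates TEAEs leading to discontinuation.

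Much of this stands. A subject who stops for a TEAE is already counted in the any-TEAE and discontinuation rows, and that event, if drug-related, continues to be followed. Only later, different events can be lost. But the 24-hour clock starts when the site becomes aware, unscheduled visits are optional, and the encouraged calls have no set frequency. None of these is a scheduled inquiry between scans. The induction and maintenance split sets no window from the last dose.

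Some stronger readings are tempting. A reader might infer that these subjects are asked about AEs only at scans, or that all of them face both a 16- and a 24-week gap. The ET Visit rules out the first. As for the second, only induction stoppers have both gaps. A reader might also infer that every non-progression stopper is affected. The rule covers only those who choose to continue, so calls would not reach consent withdrawals, losses to follow-up or deaths.

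**Conclusion.** The uneven schedule is documented and no mandatory provision closes it. After the ET Visit, non-progression stoppers who stay in the study have gaps of up to 24 weeks in scheduled AE inquiry (16 for a last dose at Week 28), against 8 weeks on the other two routes from Week 12.

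It would go too far to say that TEAEs are under-counted or that the arms are drawn together. The first depends on recall and reporting rates that the documents do not give. The second needs stopping rates or timing to differ between arms, since the rule is the same in both and the study is blinded. Under the assumed ranges, the loss is 0.05 to 3.0 points in a table row, and the shift between arms is at most 0.75 points for a 5-point difference in stopping. Safety is summarised descriptively and the primary endpoint is not affected.

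The better reason to act is safety follow-up in subjects who may have stopped for toxicity. That does not depend on any imbalance between arms. This is an inexpensive improvement worth making.

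**What to change.** **Protocol.** In Sections 4.1.1, 4.5 and 7.2, the Synopsis and Table 1-1 footnote 1, extend the 8-weekly telephone contact of Section 4.5.1 (survival, AEs, concomitant medications) to subjects who stop for a reason other than progression and stay in the study. Place the calls between the ET and scan visits, up to Week 52.

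**SAP.** In 4.11.2, add one TEAE summary by treatment group limited to onset within 8 weeks after the last dose. That point is an AE visit for stoppers (the ET Visit) and for completers (Week 36 + 8 = Week 44), so the table covers time ascertained on a comparable schedule. It makes ascertainment more even but does not equalise time on treatment. Keep the existing TEAE tables.

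**Cost.** Protocol wording, about 1 to 3 calls per affected subject using a procedure the protocol already has, and one extra table. No new site visits or tests are needed.

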4.1.2 Schedule of Assessments

An overview of the protocol visits and procedures is provided in Table 1–1. Refer to Section 8 for detailed information on each procedure and assessment required for compliance with the protocol.

The Investigator may schedule visits (unplanned visits) in addition to those listed on the schedule of activities, in order to conduct evaluations or assessments required to protect the well-being of the subject. Unscheduled visits (including reason) will be collected in the electronic case report forms (eCRF).

4.2 Discussion of Study Design

This study is designed to demonstrate the equivalence of DRL_RI to MabThera[®] in subjects with previously untreated, Stage II-IV, CD20-positive, LTB-FL, as measured by ORR.

The study will enrol subjects with LTB-FL who are asymptomatic for lymphoma specific B-symptoms. LTB-FL will be assessed according to the GELF based criteria.^{9,16} CCI

During the study, subjects will attend study visits every week (± 2 days) during the Induction Treatment Period (Weeks 1 to 4), at Week 8 (± 7 days), at Week 12 (± 7 days), thereafter every 8 weeks (± 7 days) up to Week 52 (EOS/ET Visit).

The dose of DRL_RI or MabThera[®] at 375 mg/m² of BSA will be administered as an i.v infusion.

